#### **14.1.4.3 End of post-treatment follow-up (study phase completion)**

End of post-treatment follow-up visit will be completed after discontinuation of study treatment and post-treatment evaluations but prior to collecting survival follow-up.

Patients may provide study phase completion information for one of the following reasons:

- Adverse event
- Lost to follow-up
- Physician decision
- Pregnancy
- Protocol deviation
- Technical problems
- Subject/guardian decision
- Death
- Progressive disease
- Study terminated by the sponsor

#### **14.1.4.4 Medical validation of programmed overall lesion response**

In order to be as objective as possible the RECIST programmed calculated response assessment is very strict regarding measurement methods (i.e. any assessment with more or less sensitive method than the one used to assess the lesion at baseline is considered UNK) and not available evaluations (i.e. if any target or non-target lesion was not evaluated the whole overall lesion response is UNK unless remaining lesions qualified for PD). This contrasts with the slightly more flexible guidance given to local investigators (and to the central reviewers) to use expert judgment in determining response in these type of situations, and therefore as a consequence discrepancies between the different sources of response assessment often arise. To ensure the quality of response assessments from the local site and/or the central reviewer, the responses may be re-evaluated by clinicians (based on local investigator data recorded in eCRF or based on central reviewer data entered in the database) at Novartis or external experts. In addition, data review reports will be available to identify assessments for which the investigators' or central reader's opinion does not match the programmed calculated response based on RECIST criteria. This may be queried for clarification. However, the investigator or central reader's response assessment will never be overruled.

If Novartis elect to invalidate an overall lesion response as evaluated by the investigator or central reader upon internal or external review of the data, the calculated overall lesion response at that specific assessment is to be kept in a dataset. This must be clearly documented in the RAP documentation and agreed before database lock. This dataset should be created and stored as part of the 'raw' data.

Any discontinuation due to 'Disease progression' without documentation of progression by RECIST criteria should be carefully reviewed. Only patients with documented deterioration of symptoms indicative of progression of disease should have this reason for discontinuation of treatment or study evaluation.

#### **14.1.4.5 Programming rules**

The following should be used for programming of efficacy results:

##### **14.1.4.5.1 Calculation of 'time to event' variables**

Time to event = end date - start date + 1 (in days)

When no post-baseline tumor assessments are available, the date of randomization/start of treatment will be used as end date (duration = 1 day) when time is to be censored at last tumor assessment, i.e. time to event variables can never be negative.

##### **14.1.4.5.2 Incomplete assessment dates**

All investigation dates (e.g. X-ray, CT scan) must be completed with day, month and year.

If one or more investigation dates are incomplete but other investigation dates are available, this/these incomplete date(s) are not considered for calculation of the assessment date (and assessment date is calculated as outlined in [Section 14.1.3.2.8](#)). If all measurement dates have no day recorded, the 1st of the month is used.

If the month is not completed, for any of the investigations, the respective assessment will be considered to be at the date which is exactly between previous and following assessment. If a previous and following assessment is not available, this assessment will not be used for any calculation.

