#### **Randomized treatment phase**

All eligible patients will be randomized within 7 days before Cycle 1 Day 1 to one of the two treatment arms: everolimus plus exemestane arm or placebo plus exemestane arm. Randomization will be stratified according to the presence of visceral disease and sensitivity to prior hormonal therapy status. Visceral refers to lung, liver, brain, pleural and peritoneal involvement. Sensitivity to prior hormonal therapy is defined as either (1) documented clinical benefit (complete response, partial response, stable disease  $\geq$  24 weeks) to at least one prior hormonal therapy in the advanced setting or (2) at least 24 months of adjuvant hormonal therapy prior to recurrence.

Randomized patients will start the study treatment at Cycle 1 Day 1. Patients will receive everolimus/placebo (10 mg daily oral tablets) in addition to exemestane (25 mg daily oral tablets) continuously. Dose adjustment (reduction, interruption) according to safety findings will be allowed ([Section 6.3](#)).

Patients will receive treatment until disease progression (assessed by RECIST 1.1), unacceptable toxicity, death or discontinuation from treatment for any other reason. Tumor assessments will be performed every 8 weeks after randomization until radiological progression per local assessment. Tumor assessments are to be performed every 12 weeks after data cut-off for primary analysis and as clinically indicated, until disease progression.

Imaging data used for tumor assessments during treatment phase and follow-up phase will be centrally collected, checked for quality and reviewed by a central vendor designated by

Novartis. The central review of the scans will be carried out in a blinded fashion. The decision regarding patient management will remain with the local investigator.

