### **Post-baseline imaging assessments**

Imaging assessments as described in [Table 7-2](#) should be performed at the time-points specified using the same imaging modality used at baseline, irrespective of study treatment interruption or actual dosing (see [Table 7-1](#)). Imaging assessments for response evaluation will be performed every 8 weeks ( $\pm$  7 days) after randomization. Tumor assessments are to be performed every 12 weeks after primary analysis data cut-off and as clinically indicated, until disease progression.

Additional imaging assessments may be performed at any time during the study at the investigator's discretion to support the efficacy evaluations for a subject, as necessary. Clinical suspicion of disease progression at any time requires a physical examination and imaging assessments to be performed promptly rather than waiting for the next scheduled imaging assessment.

Each lesion that is measured at baseline must be measured by the same method (either same imaging method or by photography, including a metric ruler) and when possible, the same local radiologist/physician throughout the study so that the comparison is consistent. If an off-schedule imaging assessment is performed because progression is suspected, subsequent imaging assessments should be performed in accordance with the original imaging schedule.

Combined PET/CT may be used only if the CT is of similar diagnostic quality as a CT performed without PET, including the utilization of IV contrast media. At the discretion of the Investigators, FDG-PET scans may be performed to document progressive disease per RECIST 1.1 ([Appendix 1](#)).

All study imaging (including any off-schedule imaging studies) should be submitted to the designated imaging CRO for quality control and central review.

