2.5.1 Primary endpoint

Progression-free survival (PFS) derived from an investigator's assessment of radiology data will be used as the primary efficacy variable. Disease progression for primary efficacy endpoint derivation will be assessed using the local (treating center's radiologist's) investigator's tumor assessment per RECIST 1.1.

The PFS is defined as the time from the date of randomization to the date of the first documented disease progression or death due to any cause, whichever occurs first. If a subject has not progressed or died at the analysis cut-off date, or if she receives any further anti-cancer therapy, PFS will be censored at the time of the last adequate tumor assessment before the cut-off date or the anti-cancer therapy date, whichever occurs first. Disease progression for primary efficacy endpoint derivation will be assessed using the local (treating center's radiologist's) investigator's tumor assessment. Definitions and further details on PFS can be found in Appendix 1 of the protocol.

Discontinuation due to disease progression (collected on the "End of treatment" and "End of Post Treatment Disposition eCRF page" page) without supporting objective evidence satisfying progression criteria per RECIST 1.1 will not be considered a progressive disease.

Data included in efficacy analyses

The final analysis for safety and efficacy will be conducted closeout at the end of the study. Efficacy analyses will include all data observed in subjects from the FAS regardless of whether the data were observed on-treatment or after the study treatment discontinuation until the analysis cut-off date. In particular, the "30 days" rule applied to all safety analyses will NOT be used for efficacy analyses.

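### When no investigation at a progression visit has a usable date, the protocol's incomplete-date rule usually drops the recorded progression and the patient is censored

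*Protocol*

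**What the plan says.** Protocol Section 14.1.4.5.2 starts from a data requirement: "All investigation dates (e.g. X-ray, CT scan) must be completed with day, month and year". It then covers three failures:

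- **Some dates incomplete, others available.** "If one or more investigation dates are incomplete but other investigation dates are available, this/these incomplete date(s) are not considered for calculation"; the assessment is dated from the remaining investigations.
- **Day missing on every measurement.** The first of the month is used.
- **Month missing.** "If the month is not completed, for any of the investigations, the respective assessment will be considered to be at the date" halfway between the neighbouring assessments. If that is not possible: "If a previous and following assessment is not available, this assessment will not be used for any calculation".

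The surrounding rules decide what follows:

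- Protocol 14.1.3.2.8 dates a PD assessment at its earliest measurement. It defines the last adequate assessment as the last one with CR, PR or SD.
- Protocol 4.1, Randomized treatment phase: "Tumor assessments will be performed every 8 weeks after randomization until radiological progression per local assessment". Section 7.1.6.2 stops post-treatment scanning at investigator PD as well. Table 7-1 waives the end-of-treatment (EOT) scan if the previous scan was within 28 days.
- Protocol 10.4.3 and SAP 2.5.3 keep a PFS event that follows one missing assessment and censor one that follows two or more.
- SAP 2.5.1: "Definitions and further details on PFS can be found in Appendix 1 of the protocol". SAP 5.4 has imputation rules for study drug, adverse event, medication and death dates, and none for tumour assessments.

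**The concern.** The month rule needs a scan on each side. A stable-disease scan in mid-study normally has both, so it is kept with an approximate date. A progression scan is normally the last one, so it lacks the following neighbour and is discarded. The assessment most likely to be lost is therefore the one that defines the primary endpoint. Progression is known to have occurred and to lie after the previous scan; only its exact date is unknown. The rule responds by treating the patient as not having progressed.

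The trigger for the rule is also unclear. The section first says to ignore incomplete dates if others are available, then applies the month rule when the month is missing for any of the investigations. Two programmers could code a visit with one good date and one bad date differently, one obtaining an event and the other a censoring.

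Nothing later in the plan would expose a lost event: SAP 2.5.4 plans no sensitivity analysis for the final report, and SAP 1.2 does not repeat the central-review analyses.

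**Working it through.** **1. Trace of the rule.** Take a hypothetical patient on the 8-week schedule: SD at weeks 8 and 16, PD at week 24. A date is usable here if at least its month and year are recorded. A dropped PD visit is counted as one missing assessment.

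| Situation at the week-24 PD visit | Incomplete dates ignored when others exist | Month rule triggered by any one missing month |
|---|---|---|
| One of two dates lacks the month | PD event, week 24 | Dropped, censored at week 16 |
| No usable date, no later scan | Dropped, censored at week 16 | Dropped, censored at week 16 |
| No usable date, death at week 30, no new therapy | Death event, week 30 (one missing assessment) | Same |
| No usable date, death at week 40 | Censored at week 16 (weeks 24 and 32 missing) | Same |
| No usable date, later scan at week 28 | PD event at (16 + 28)/2 = week 22 | Same |

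The first row is the wording conflict. The second and fourth rows show the loss of a recorded progression, and it occurs under both readings. The third and fifth rows show when the patient still has an event.

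The final clause has a further ambiguity. If it excludes an assessment only when neither neighbour is available, the case with one neighbour, which is the usual position of a PD scan, has no rule at all.

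**2. Scale.** Protocol 10.6 gives 110 events and, at HR 0.62, a 90% CI of 0.45 to 0.85. With 1:1 allocation, SE(log HR) ≈ 2/√d, so the CI is HR × exp(±1.645 × 2/√d).

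- Plan's figure: 2/√110 = 0.1907; 1.645 × 0.1907 = 0.3137; exp(0.3137) = 1.368; 0.62/1.368 = 0.453 and 0.62 × 1.368 = 0.848. The stated interval is reproduced.
- One lost progression: 1/110 = 0.9% of the events.
- The documents give no rate of missing months. Assuming a number lost and holding the HR at 0.62:

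| Events lost (assumed) | 90% CI |
|---|---|
| 0 | 0.453 to 0.848 |
| 1 | 0.452 to 0.850 |
| 2 | 0.452 to 0.851 |
| 5 | 0.450 to 0.855 |
| 11 | 0.445 to 0.863 |

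These rows show precision only. A shift in the estimate itself would depend on the arms in which the losses fell, which cannot be known from the documents.

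**The case against.** **A single missing month.** A reader might infer that one missing month on one investigation is enough to lose a progression. The documents do not support that as the intended rule. The section first sets incomplete dates aside when others exist, and its day rule applies only when all measurements lack the day. In that sequence the month rule most naturally covers visits where no investigation has a usable date. What stands is that the literal wording conflicts with the earlier instruction and should be repaired.

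**Always dropped, always censored.** This too goes further than the text. A following scan can exist: an equivocal new lesion is confirmed on repeat imaging and dated back (14.1.2.4.4), a patient may be assessed after progression while still on treatment (14.1.3.1), and an EOT scan is waived only within 28 days. A death after one missing assessment, before new anticancer therapy, remains an event.

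**A bias favouring one arm.** Replacing an event by an earlier censoring tends to lengthen estimated PFS in the arm where it happens. The trial is double-blind, and nothing in the documents suggests that dates go missing more often in one arm. The rule also drops a final SD scan that has no successor, which costs follow-up time but no event.

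**PD dated before an SD scan in the same month.** The first-of-month rule for a missing day might seem to invite this. Scheduled scans are 8 weeks apart ±7 days, so at least 56 − 14 = 42 days apart, and two of them cannot share a calendar month. An unscheduled scan would be needed.

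**Prevention.** Complete dates are mandatory, missing values are queried (Protocol 9.4), and Appendix 1 calls its programming section guidance. This makes cases rare. It does not supply a correct rule for those that remain, and Section 14.1.4.5 says its rules should be used for programming efficacy results.

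**Conclusion.** The point holds in a narrow form. When no investigation at a PD visit has a usable date and there is no later scan, the stated rule discards a recorded progression and the patient is censored at the last adequate assessment, unless a qualifying death supplies the event. No SAP rule corrects this. Separately, the trigger for the month rule is worded inconsistently within its own section.

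The likely effect is small: 0.9% of 110 events per lost progression, and a 90% CI of 0.450 to 0.855 even if five were lost at an unchanged HR. The number affected is unknown and may be zero.

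The conclusion applies to the final PFS analysis, which this SAP governs. The primary analysis was reported at the May 2020 cut-off. The plan that governed it is not among the documents, so whether it had its own tumour-date rule cannot be judged. The 110 is the planned primary count; if more events have accrued by the final cut-off, each one is a smaller share.

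**What to change.** Add to SAP 2.5.3, for the final PFS analysis:

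- **(a)** If any investigation at the visit has a complete date, use the complete dates only. Apply the month rule only when no investigation has a usable date.
- **(b)** Where the imaging CRO holds the scan, take the date from its record. Protocol 7.2.1 says: "All study imaging (including any off-schedule imaging studies) should be submitted to the designated imaging CRO for quality control and central review". Central review stops once the primary event count is reached, so this source may not cover later scans, and (c) is still needed.
- **(c)** Never drop a recorded PD. If it has no following assessment, keep it as an event dated between the last adequate assessment and the earliest of EOT, new anticancer therapy, death or cut-off that falls after that assessment. The condition matters because patients who stop treatment without PD continue to be scanned, so EOT can precede the last adequate scan. The midpoint of that interval would follow the Appendix's own convention; whichever point is chosen should be fixed before database lock.
- **(d)** If the first of the month is kept for a missing day, require that the imputed date is not earlier than the day after the previous assessment.

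Report the number of assessments dated under each rule, by arm. The cost is a few lines of SAP text, a small programming change and, for (b), a date check against the CRO record for any affected visit.

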##### **14.1.4.5.3 Incomplete dates for last known date patient alive or death**

All dates must be completed with day, month and year. If the day is missing, the 15th of the month will be used for incomplete death dates or dates of last contact.

##### **14.1.4.5.4 Non-target lesion response**

If no non-target lesions are identified at baseline (and therefore not followed throughout the study), the non-target lesion response at each assessment will be considered 'not applicable (NA)'.

##### **14.1.4.5.5 Study/project specific programming**

The standard analysis programs need to be adapted for each study/project.

##### **14.1.4.5.6 Censoring reason**

In order to summarize the various reasons for censoring, the following categories will be calculated for each time to event variable based on the treatment completion page, the study evaluation completion page and the survival page.

For survival the following censoring reasons are possible:

- Alive
- Lost to follow-up

For PFS and TTP (and therefore duration of responses) the following censoring reasons are possible:

- Ongoing without event
- Lost to follow-up
- Withdraw consent
- Adequate assessment no longer available\*
- Event documented after two or more missing tumor assessments (optional, see [Table 14-5](#))
- Death due to reason other than underlying cancer (*only used for TTP and duration of response*)
- Initiation of new anti-cancer therapy

\* Adequate assessment is defined in [Section 14.1.3.2.8](#). This reason is applicable when adequate evaluations are missing for a specified period prior to data cut-off (or prior to any other censoring reason) corresponding to the unavailability of two or more planned tumor assessments prior to the cut-off date. The following clarifications concerning this reason should also be noted:

- This may be when there has been a definite decision to stop evaluation (e.g. reason="Sponsor decision" on study evaluation completion page), when patients are not followed for progression after treatment completion or when only UNK assessments are available just prior to data cut-off).
- The reason "Adequate assessment no longer available" also prevails in situations when another censoring reason (e.g. withdrawal of consent, loss to follow-up or alternative anti-cancer therapy) has occurred more than the specified period following the last adequate assessment.
- This reason will also be used to censor in case of no baseline assessment.

This document describes the detailed statistical methodology of the Statistical Analysis Plan (SAP) for the final Clinical Study Report (CSR) at the end of CRAD001Y2202: A randomized, double-blind, placebo controlled, phase II study of Everolimus in combination with Exemestane in the treatment of Chinese postmenopausal women with estrogen receptor (ER) positive, HER-2 negative, locally advanced, recurrent, or metastatic breast cancer after recurrence or progression on prior letrozole or anastrozole. The data will be analyzed by Novartis. It is planned that data from all centers that participate in this study will be used. This document refers to the study protocol Version 1.0 dated May 23 2017. The the indication of “Postmenopausal women with advanced hormone receptor-positive, HER2-negative breast cancer in combination with exemestane after failure of treatment with letrozole or anastrozole” has been approved by the Chinese Health Authorities February 09 2022.

1.1 Study design

This is a multicenter, double-blind, randomized, placebo-controlled, phase II study evaluating treatment with everolimus (10 mg daily) versus placebo in combination with exemestane (25 mg daily) in Chinese postmenopausal women with locally advanced, recurrent or metastatic ER positive HER2-negative breast cancer refractory to non-steroidal aromatase inhibitors.

Approximately 160 subjects will be randomized in 1:1 ratio to receive either everolimus or matching placebo in a blinded manner in addition to open label exemestane (25 mg daily tablets).

All eligible subjects will be randomized within 7 days before Cycle 1 Day 1 to one of the two treatment arms: everolimus plus exemestane arm or placebo plus exemestane arm. Randomization will be stratified according to the presence of visceral disease and sensitivity to prior hormonal therapy status. Visceral refers to lung, liver, brain, pleural and peritoneal involvement.

Randomized subjects will start the study treatment at Cycle 1 Day 1. Subjects will receive everolimus/placebo (10 mg daily oral tablets) in addition to exemestane (25 mg daily oral tablets) continuously.

Subjects will receive treatment until disease progression (assessed by RECIST 1.1), unacceptable toxicity, death or discontinuation from treatment for any other reason. Tumor assessments will be performed every 8 weeks after randomization until radiological progression per local assessment.

There won't be any interim analysis for this study.

1.2 Study objectives and endpoints

The primary objective is to assess the progression-free survival (PFS) as determined by investigator assessment of everolimus plus exemestane and of placebo plus exemestane.

The secondary objectives are:

- To assess PFS in the two treatment arms as determined by a Blinded Independent Review Committee (BIRC)

- To assess overall survival (OS) in the two treatment arms
- To assess the following efficacy endpoints in the two treatment arms based on both local investigator's assessment and BIRC
 - Overall response rate (ORR)
 - Clinical benefit rate (CBR)
 - Time to response and duration of response
- To assess time to deterioration of ECOG Performance Status (PS)
- To characterize the safety and tolerability of everolimus and exemestane versus placebo and exemestane
- Characterize the pharmacokinetics of everolimus pre-dose concentration (C_{min}) and concentration at 2 hours post dose (C_{2h}) when administered in combination with exemestane
- Compare the two treatment arms with respect to pre-dose concentration (C_{min}) and concentration at 2 hours post dose (C_{2h}) of exemestane and to compare the two treatment arms with respect to estradiol (E2) changes from baseline.

For secondary objectives with regards to BIRC assessment and PK analyses, the analysis will not be repeated for the final CSR as per protocol. The results were addressed in the primary CSR (DCO:19-May-2020).

2 Statistical methods

